8.6 Safety Oversight

All safety data will be reported to sponsor, DSMB, IRB, and FDA every six months, or, in the case of any major safety concern or question, immediately. The Principal Investigator will assume primary responsibility for all safety oversight.

9 CLINICAL MONITORING

Subjects will be monitored for safety at baseline pre-infusion, 1 hour after infusion begins, 1 hour after infusion is discontinued, and then during follow-up visits 1-day and 1-, 2-, 4- and 8-weeks post-infusion. Safety monitoring at each time point will include physical examination, vital sign monitoring, laboratory assessments, electrocardiography, and AE/tolerability monitoring. Our preliminary phenotyping studies characterizing cognitive and adaptive functioning in Phelan McDermid syndrome suggest that these children and adults have intellectual disability. This patient population is significantly delayed in receptive language, expressive language, and overall functional communication skills. As such, it is impossible to directly query these subjects using verbal methods with respect to safety and tolerability. Instead, we rely on parent report using open-ended methods, in addition to physical exams and laboratory measures.

Clinical monitoring for efficacy will occur at baseline, 1-hour post-infusion, 1-day post-infusion, and 1-, 2-, 4-, and 8-weeks post-infusion.

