Urinalysis	X	Х		Х	X	X	
Pregnancy Test ³	X	Х		X	X	X	
Sample for Pharmacokinetic		X					
Analysis ⁴		Λ					
Sample for Assessment of		Х		X		X	
Phosphorylated ERK levels ⁵				Λ		Λ	
Administer Study Medication ⁶		Х					
Seizure Diary Dispense/Review	X	Х		Χ	Х	Х	
CGI-S	X	Х		X	Х	X	
CGI-I		Х		Χ	Х	X	
Clinician Completed PMS	X	Х		X	X	X	
Domain Specific Causes for	Λ	Λ		Λ	Λ	Λ	
Concern VAS							
Sensory Adjustment for							
Neurodevelopmental Disorders		X		Х	X	X	
(SAND)							
Caregiver Top 3 Concerns		Х		X	X	X	
Aberrant Behavior Checklist		Х		X	X	X	
(ABC)							
Repetitive Behavior Scale-		Х		X	X	X	
Revised (RBS-R)							
Electroencephalography	X		X	X	X		
Computerized eye tracking	X	Х	X	X	X	X	
Auditory Evoked Potential	X	Х	X	X		X	

Visual Evoked Potential	X	Х	X	X		X	
Adverse Events ⁷	X	X		X	X	X	X
Concomitant Medications	X	Х		X	X	X	X
Telephone questionnaire							X

- 1. Vital Sign Measures include Heart Rate, Respiratory Rate, Blood Pressure, Temperature, Height, and Weight
- 2. Clinical labs standardly include i) Full Blood Count with differential, ii) Biochemistry panel. When marked with an "a", a lipid panel will also be collected
- 3. Urine or serum pregnancy test for female subjects of child bearing potential
- 4. Pharmacokinetic sample (6 mL) will be taken at approximately 2 hours and approximately 6 hours after the start of the infusion as well as 1 hour after the cessation of the study drug.
- 5. 6 mL blood sample required for assessment of phosphorylated ERK levels
- 6. A single 6-hour intravenous treatment will be given to subjects, with total dose administered 120 mg/m²
- 7. Adverse Events (AEs) and Serious Adverse Events (SAE's) will be collected from the time of informed consent.
- 8. Baseline procedures outlined in Table 2, Baseline Visit Schedule of Events

Table 2: Baseline Visit Schedule of Events

Baseline Procedures	Pre-Infusion ¹⁰	During Infusion	Post-Infusion ⁹
V2			
Week 0			
Eligibility Criteria	Х		
Physical Examination ¹	Х	X	X ^a
Vital Sign Measures ²	Xb	X	X
ECG	Х	X ³	
Clinical Labs ⁴	X		
Urinalysis	Х		
Pregnancy Test ⁵	Х		
Sample for Pharmacokinetic Analysis ⁶	X	Х	X
Sample for Assessment of Phosphorylated ERK levels ⁷	X	X	
Administer Study Medication ⁸		X	
Seizure Diary Dispense/Review	Х		
CGI-S	Х		
CGI-I			X
Clinician Completed PMS Domain Specific Causes for Concern VAS	X		
Sensory Adjustment for Neurodevelopmental Disorders (SAND)	X		
Caregiver Top 3 Concerns	Х		
Aberrant Behavior Checklist (ABC)	Х		

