Repetitive Behavior Scale- Revised (RBS-R)	Х		
Electroencephalography			
Computerized eye tracking	X		
Auditory Evoked Potential	X		
Visual Evoked Potential	X		X
Adverse Events	X	Х	X
Concomitant Medications	X	Х	X

1. When marked with a) a brief physical examination is acceptable

2. Vital Sign Measures include Heart Rate, Respiratory Rate, Blood Pressure, Temperature. When marked with b) Height, and Weight are also measured

3. ECG during infusion to be completed between 4-6 hours after infusion start

4. Clinical labs standardly include i) Full Blood Count with differential, ii) Biochemistry panel

5. Urine or serum pregnancy test is sufficient

6. Pharmacokinetic sample (6 mL) will be taken pre-infusion and at approximately 2 hours and approximately 6 hours after the start of the infusion as well as 1 hour after the cessation of the study drug.

- 7. 6 mL blood sample required for assessment of phosphorylated ERK levels will be taken pre-infusion and at approximately 2 hours and approximately 6 hours after the start of the infusion as well as 1 hour after the cessation of the study drug.
- 8. A single 6-hour intravenous treatment will be given to subjects, with total dose administered 120 mg/m^2
- 9. Post-infusion assessments will occur one hour after infusion prior to discharge with the exception of EEG which occurs the following day in the AM
- 10. If required for scheduling, pre-infusion assessments can be completed one day prior to the infusion

ii. Table of Contents

i. I	Protocol Synopsis	4
ii.	Table of Contents	14
LIS	ST OF ABBREVIATION	19
iii.	. Table of Tables	20
iv.	SCHEMATIC OF STUDY DESIGN	20
1.	KEY ROLES	21
2.	INTRODUCTION: BACKGROUND INFORMATION AND SCIENTIFIC RATIONALE	23
,	2.1 Background Information	23
	2.1.1 Phelan McDermid Syndrome (PMS)	23
,	2.1.2 AMO-01 and Rationale for Clinical Investigation	23
,	2.1.3 Pre-Clinical Research	25
2.1	1.4 Non-Clinical Pharmacology	25
2.1	1.5 Non-Clinical Pharmacokinetics, Metabolism and Interactions	26
2.1	1.6 Non-Clinical Toxicology	27
2.1	1.7 Clinical Experience	28
2.1	1.8 Safety Summary	28
2.2	2 Rationale	29
2.3	3 Potential Risks and Benefits:	33
3.	OBJECTIVES AND PURPOSE	34
4.	Study Design and Endpoints	34
4	4.1 Description of the Study Design	34
4	4.2 Study Endpoints	35
	4.2.1 Primary Endpoint:	35
	4.2.2 Secondary Endpoints:	35
4	4.2.3 Exploratory Endpoints:	35
5.	Study Enrollment and Withdrawal	36
	5.1 Participant Inclusion Criteria	36
	5.2 Participant Exclusion Criteria	36

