6.2 Study Agent Accountability Procedures

In accordance with regulatory requirements, the Investigator or designated site staff must document the amount of IMP received from AMO Pharma. Following receipt they should document the amount of IMP dispensed and/or administered to study subjects and the amount returned to the pharmacy. Product accountability records must be maintained throughout the course of the study.

At the end of the study, all IMP will be reconciled and all remaining materials will be destroyed by the site according to the sponsor's instruction once it has been inventoried and drug accountability records reviewed. All destroyed IMP must have a documented proof of destruction.

7 Study Procedures and Schedule

Refer to Table 1 for an overall schedule of assessments for each visit. Refer to Table 2 for a detailed schedule of assessments to be completed on V2.

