7.3.3 Follow-up

Planned follow-up visits will occur at 1 day (V3), week 1 (V4), and week 2 (V5) post-dose. A follow-up phone call will occur 8 weeks post-dose. Refer to the schedule of events (Table 1) for a list of assessments to be completed at each follow-up visit.

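### Table 1 schedules no safety assessment on Day 1, and the tables put no safety labs or ECG between the infusion and Week 1, contrary to Sections 9, 7.2.1 and 8.3

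*Combined protocol and SAP*

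**What the plan says.** Section 9 (Clinical Monitoring) places safety monitoring before the infusion, then "1 hour after infusion begins, 1 hour after infusion is discontinued, and then during follow-up visits 1-day and 1-, 2-, 4- and 8-weeks post-infusion". On content it says: "Safety monitoring at each time point will include physical examination, vital sign monitoring, laboratory assessments, electrocardiography, and AE/tolerability monitoring". Because subjects cannot be asked directly about tolerability, it adds: "Instead, we rely on parent report using open-ended methods, in addition to physical exams and laboratory measures".

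Two other sections agree with part of this. Section 7.2.1 calls for biochemistry and a full blood count at screening and at every clinic visit. Section 8.3 has the investigator ask about adverse events at every visit or contact.

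The schedule that sites are told to use reads differently. Section 7 says "Refer to Table 1 for an overall schedule of assessments for each visit", and Section 7.3.3, which names V3 as the Day 1 visit, says "Refer to the schedule of events (Table 1) for a list of assessments to be completed at each follow-up visit". Section 7.1.7 likewise ties ECGs after screening to the schedule of assessments. In Table 1 the V3 column is filled only for EEG, eye tracking, auditory evoked potential and visual evoked potential. It is empty for physical examination, vital signs, ECG, clinical labs, urinalysis, pregnancy test, adverse events and concomitant medications. Footnote 7 says adverse events "will be collected from the time of informed consent", yet that row has no entry at V3.

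Table 2 (the infusion day) has clinical labs and urinalysis before the infusion only. It has an ECG before the infusion and one during it: "ECG during infusion to be completed between 4-6 hours after infusion start". One hour after the infusion it has a brief examination, vital signs and adverse events, but no lab or ECG. Its footnote 9 reads: "Post-infusion assessments will occur one hour after infusion prior to discharge with the exception of EEG which occurs the following day in the AM". Footnote 10 allows the pre-infusion assessments to be done the day before.

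**The concern.** The text and the tables cannot both be followed. A site that works from the tables does no safety check on Day 1, although the subject is in the clinic, and takes no post-dose safety bloods until Week 1. A site that works from Sections 9 and 7.2.1 does both. With two sites, the data could differ by site.

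Section 4.2.1 makes the incidence of abnormal labs, ECGs and vital signs one of two primary endpoints, and there is only one dose, so the first days cannot be observed again. On the tables' path, scheduled tests would miss:

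- laboratory changes that appear after dosing and resolve before Week 1;
- ECG changes between the 4-6 hour tracing and Week 1;
- vital-sign or examination changes between discharge and Week 1.

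The laboratory criterion in Section 8.5 (grade 3 or higher at any time) would have no scheduled post-dose data before Week 1. The grade 4 rule for any adverse event still operates on clinical events. The protocol says it leans on examinations and laboratory measures because verbal report is not available, so the blank cells concern the tests it most depends on.

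**Working it through.** No sample size, power or error rate depends on this point. The check compares Section 9 with the two tables cell by cell, then takes time differences.

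**Step 1. Section 9 grid: eight time points by five items.** Weeks 1, 2 and 4 and Day 1 are read from Table 1; the infusion day is read from Table 2. The ECG at 4-6 hours is credited to Section 9's point during the infusion.

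| Time point | Exam | Vital signs | Labs | ECG | AE | Scheduled |
|---|---|---|---|---|---|---|
| Pre-infusion | yes | yes | yes | yes | yes | 5 |
| During infusion | yes | yes | no | yes (4-6 h) | yes | 4 |
| 1 h after infusion | yes (brief) | yes | no | no | yes | 3 |
| Day 1 (V3) | no | no | no | no | no | 0 |
| Week 1 | yes | yes | yes | yes | yes | 5 |
| Week 2 | yes | yes | yes | yes | yes | 5 |
| Week 4 | yes | yes | yes | yes | yes | 5 |
| Week 8 (telephone) | no | no | no | no | yes | 1 |

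Total: 5 + 4 + 3 + 0 + 5 + 5 + 5 + 1 = 28 of 40. Section 4.1 makes Week 8 a telephone call, so four of Section 9's five items cannot be done there. Without that row the count is 27 of 35, leaving 8 unscheduled cells: five at Day 1, two at 1 hour after the infusion (labs, ECG) and one during it (labs).

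Over the three time points in the first day after dosing starts, the tables schedule labs at 0 of 3, ECG at 1 of 3, and examination, vital signs and adverse events at 2 of 3 each.

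**Step 2. Intervals to the Week 1 assessment.** The protocol gives no visit windows. I assume V3 at 24 h and Week 1 at 168 h from the start of infusion, with the last infusion-day check at 6 + 1 = 7 h.

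- Labs: (168 - 0)/24 = 7.0 days; if drawn the day before, (168 + 24)/24 = 8.0 days.
- ECG: (168 - 6)/24 = 6.75 days to (168 - 4)/24 = 6.83 days.
- Vital signs and examination: (168 - 7)/24 = 6.71 days.

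**Step 3. The same intervals with V3 marked.**

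- Labs: 24/24 = 1.0 day, or (24 + 24)/24 = 2.0 days.
- ECG: (24 - 6)/24 = 0.75 day to (24 - 4)/24 = 0.83 day.
- Vital signs and examination: (24 - 7)/24 = 0.71 day.

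The longest interval up to Week 1 without labs, ECG, vital signs or examination then becomes (168 - 24)/24 = 6.0 days, from Day 1 to Week 1. The change therefore covers the first day, not the whole week.

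**The case against.** The strongest reply is that this is a discrepancy between text and tables rather than a true monitoring gap. Sections 7.2.1 and 8.3 already require Day 1 labs and adverse-event enquiry, and the tables are known to under-report: as it reads, Table 2 has no post-infusion mark for pERK, although its own footnote 7 requires that sample. The blank V3 column may be clerical. That is plausible. But Sections 7, 7.3.2, 7.3.3 and 7.1.7 send sites to the tables, so a clerical blank would still be followed.

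Second, for ECG, vital signs and examination at V3 the only textual support is Section 9, which is itself wrong at Week 8 and does not match Table 2 for the tests it sets 1 hour into the infusion. This stands: the case for labs and adverse events is firmer than for the other three items. Likewise, three of the eight unscheduled cells disappear once Section 9 is aligned with Table 2, leaving the five at Day 1.

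Third, the halting-rule consequence is modest. The study gives one dose, so a Day 1 result cannot stop further dosing of that subject. A grade 3 laboratory finding halts the study only when two patients meet stopping conditions. With up to 10 subjects over about 20 months (October 2017 to June 2019), even spacing gives roughly one every 20/10 = 2 months. Earlier detection would matter mainly if subjects were dosed close together, and I found no stated minimum interval.

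Fourth, adverse-event capture is largely preserved: each visit asks about events since the last one (Section 7.1.5), events are recorded through the Week 8 call, and unscheduled safety visits are allowed. Labs, vital signs and ECGs in the Phase I oncology study were generally unremarkable (Section 2.1.8.1), laboratory changes in Phase II were minimal (2.1.8.2), and the dose here is one-fourth of the daily dose given there in 14-day cycles (2.2.1). All this makes a large missed signal less likely. It does not exclude one in a new population, and neither recall nor symptom-driven visits detect silent laboratory or ECG changes.

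**Conclusion.** The concern holds. Table 1 leaves the Day 1 visit without any safety assessment, and Table 2 has no safety lab after dosing and no ECG after the infusion, in contradiction to Section 9 (all five items), Section 7.2.1 (labs) and Section 8.3 (adverse events). If sites follow the tables, the interval to Week 1 is 7 to 8 days for labs, 6.75 to 6.83 days for ECG and 6.7 days for vital signs and examination.

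These figures rest on nominal visit times and on the tables taking precedence over the text. The infusion day itself is monitored by examination, vital signs, adverse-event enquiry and an ECG at 4-6 hours, so the weakness is confined to post-dose labs and to the period between discharge and Week 1. It should be corrected because it affects a primary safety endpoint after a dose given once; it does not invalidate the design.

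**What to change.** In Table 1, mark V3 for adverse events, concomitant medications, vital signs, physical examination, ECG and clinical labs. Labs and adverse events follow from Sections 7.2.1 and 8.3 as well as Section 9; the examination, vital signs and ECG from Section 9; concomitant medications from consistency with the other visits. Section 7.2.1 also asks for a pregnancy test at every clinic visit after screening, so either mark V3 for it or reword that sentence.

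In Section 9, replace the labs and ECG at 1 hour into the infusion with the Table 2 schedule (ECG at 4-6 hours), align the entry for 1 hour after the infusion with Table 2, and restrict Week 8 to adverse-event and concomitant-medication enquiry by telephone. Optionally, add a safety-lab tube to the PK and pERK draw already taken 1 hour after the infusion.

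The cost is a schedule amendment with no added visit, since subjects already return the next morning for EEG. Each subject has one routine blood draw, one triplicate ECG, vital signs and an examination at V3. For up to 10 subjects that is at most 10 draws and 10 x 3 = 30 tracings. The optional tube adds a small volume to a day that already takes 4 x (6 + 6) = 48 mL for PK and pERK.

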10 STATISTICAL CONSIDERATIONS

10.1 Statistical and Analytical Plans

All details of the statistical analyses will be described in a separate study specific 'Statistical Analysis Plan' (SAP), which will be finalized before the clinical data base is declared clean and locked. Baseline for all comparisons will be the measurements obtained as close as possible before administration of the study drug.

10.2 Statistical Hypotheses

We hypothesize that the medication will be safe and tolerable as determined by the absence of SAEs and propose that at least 70% of participants enrolled will be able to complete the infusion.

We hypothesize that, when relevant, seizures will be reduced in frequency by at least 25% compared with 'baseline.' More explicitly, the null (H0) and alternative (Ha) hypothesis will be defined as

H0: The average number of weekly seizures at follow-up (week 4) are reduced by less than 25% compared to baseline

Ha: The average number of weekly seizures at follow-up (week 4) are reduced by at least 25% compared to baseline

We hypothesize that EEG abnormalities will be reduced in frequency by at least 25% compared with 'baseline.' More explicitly, the null (H0) and alternative (Ha) hypothesis will be defined as

H0: The average number of EEG abnormalities at follow-up (week 2) are reduced by less than 25% compared to baseline

Ha: The average number of EEG abnormalities at follow-up (week 2) are reduced by at least 25% compared to baseline

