Statistical Methods:	Safety and tolerability aspects of the data will be tabulated. An adverse event (AE) will be defined as any untoward medical occurrence in a study subject, temporally associated with the use of the experimental medication, whether or not considered related to the medication. An

	 adverse event can therefore be any unfavorable and unintended sign (including an abnormal laboratory finding), symptom, or disease (new or exacerbated) temporally associated with the use of the experimental medication. A serious adverse event (SAE) will be defined as an AE that meets any of the following criteria: results in death; is life threatening; requires inpatient hospitalization; results in a persistent or significant disability/incapacity; any other adverse event that, based upon appropriate medical judgment, may jeopardize the subject's health and may require medical or surgical intervention to prevent one of the outcomes listed above
	For the assessment of efficacy, to test the hypothesis of no differences in the mean between baseline, week 1, and week 4 we will examine the data distributions of the primary and secondary efficacy variables. The primary analysis and study evaluation will be based on the 10 subjects recruited for this study. All tests of statistical hypothesis will be done on the two-sided 5% level of significance and presented together with the associated point estimate and two-sided 95% confidence interval.
	Since the study participants are expected to have very differing degrees of baseline signs and symptoms, the evaluation of treatment effects will include an adjustment for the pre-treatment baseline level in each treatment period. For this purpose, the differences against baseline will be analysed.
	Since this is an initial proof-of-concept study that is exploratory in nature, no multiplicity-related adjustments will be made in the reported p-values.
	The SAS software, proc npar1way or similar R software will be used to fit the statistical models.
Phase:	Phase IIa
Number of Sites enrolling participants:	2
Description of Study Agent:	AMO-01 (INN: diazepinomicin), formerly known as ECO-4601 and TLN-4601, is a low molecular weight, brain penetrating, structurally novel, farnesylated dibenzodiazepinone.

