4.1 Description of the Study Design

This is an open-label study to investigate the safety, tolerability and efficacy of a single 6-hour intravenous infusion of AMO-01 to treat adolescents and adults with PMS and co-morbid epilepsy. The subjects in this study will be administered the experimental study medication and then be followed up to ascertain safety and tolerability, and to determine whether their seizure frequency, as well as their signs and symptoms of PMS, are improving, using a caregiver-completed seizure diary as well as accepted rating scales and functional measures in addition to clinical EEG. Approximately 15 subjects will be screened and up to 10 subjects will receive study medication.

The study will have 4 phases (Figure 1, Study Design):

- Screening (Weeks -4 to -1): Subjects will be screened to ensure adherence to eligibility criteria and to assess pre-medication seizure frequency
- Baseline (Day 0): Subjects will complete baseline assessments in-clinic prior to study drug administration
- Study Drug Administration (Day 0): Eligible subjects will receive a single 6-hour intravenous infusion at a single dose of 120 mg/m²
- Follow-up (+1 day Week 8): follow-up visits will occur at 1 day after and 1, 2 and 4 weeks after receiving study medication. A phone call will occur 8 weeks after receiving study medication.

• .

Figure 1: Study Design

V	1	V2	V3	V4	V5	V6	Phone FU
- 1		Baseline					
	Week -4 to -1	Day 0 Study Drug	Day 1	Week 1	Week Z	Week 4	Week 8
	Screening	Administration Single 6-hour IV Infusion dose of 120mg/m ²			Follow-up		

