The study will be halted* if two patients experience stopping conditions across sites. Any patient experiencing stopping conditions will be reported to the PI/Sponsor immediately (Exceptions for this criterion: Patients who withdraw voluntarily for reasons not directly related to or intrinsic to the study, e.g. incidental considerations such as concerns about travel time to study visits, unexpected pregnancy in the family, etc.). In addition, the study will be halted if one patient experiences a serious related adverse effect (grade \geq 4 AE).

All safety data will be reported to the PI/Sponsor, DSMB, IRB, and FDA every six months, or, in the case of any major safety concern or question, immediately. If any study stopping condition occurs, this will be reported immediately and the study halted, pending review by DSMB, IRB, and FDA, and until the decision by regulatory authorities to resume, suspend or close the study has been made.

*Operationally, "halting" will ordinarily mean that no further screening of new subjects and no treatment initiation will occur until the safety issue has been investigated and resolved (i.e., a final decision has been made to resume, suspend or close the study has been made). Enrolled study participants who have no new symptoms or adverse effects will ordinarily be allowed to continue study observation or treatment without interruption while the safety issue is being investigated, unless it is the contemporaneous judgment of the PI or

subsequent judgment of the DSMB, IRB, or FDA that it is unsafe to do so, in which case all observation or treatment interventions will be suspended forthwith.

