10.4.2 Analysis of the Primary Endpoint(s)

Adverse events (AEs) will be tabulated. Changes in rates of particular groups of AEs from baseline to follow-up may be formally examined calculating the McNemar test.

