10.5 Sample Size

The sample size was not based on any statistical criteria but what was pragmatic and achievable, given that PMS is a rare disease. See section "Strategies for Recruitment and Retention".

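### With at most 10 dosed subjects, neither zero SAEs nor 70% infusion completion supports a conclusion that AMO-01 is safe and tolerable

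*Combined protocol and SAP*

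**What the plan says.** The primary objective (Section 3) is safety and tolerability from Baseline through Week 8. Section 4.2.1 names two primary endpoints: incidence of AEs including SAEs, and incidence of abnormal findings in objective assessments such as laboratory values, ECGs and vital signs.

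Section 10.2 attaches two criteria to this objective, an SAE criterion and a completion target. It hypothesises that the drug will be "safe and tolerable as determined by the absence of SAEs and propose that at least 70% of participants enrolled" will complete the infusion. Neither has a null and alternative hypothesis, although the seizure and EEG hypotheses in the same section do.

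For the analysis, Section 10.4.2 says "Adverse events (AEs) will be tabulated" and allows an optional McNemar test on groups of AEs. Section 10.4.1 adds summary statistics. Section 10.4 sets a general convention of two-sided 5% tests with two-sided 95% confidence intervals, but names no method for a proportion.

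On numbers, Section 4.1 says "up to 10 subjects will receive study medication", the synopsis says "The primary analysis and study evaluation will be based on the 10 subjects recruited for this study", and Section 10.5 says "The sample size was not based on any statistical criteria but what was pragmatic and achievable".

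**The concern.** Section 10.2 makes the absence of SAEs the thing that determines safety and tolerability. A reader who follows it could report the primary objective as met after 0/10 SAEs and 7/10 completed infusions. With 10 subjects those results are compatible with a substantial SAE risk and with a completion rate well below 70%.

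The SAE criterion also errs in the other direction. Section 8.1.1 defines an AE without regard to causality, and Section 8.1.2 makes inpatient hospitalization serious. In an epilepsy population followed for 8 weeks, a single admission unrelated to the drug would refute the hypothesis.

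At stake is what the trial may claim on its primary objective in a first study of this drug in PMS.

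**Working it through.** The plan gives no precision or error rate for either criterion, so there is no figure of its own to reproduce.

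**Inputs.** n = 10, the maximum dosed (Section 4.1). SAE criterion: 0 events. Completion target: 70%, which is 7/10 if all 10 are dosed (Section 10.2). Confidence level: two-sided 95% (Section 10.4). The true risks and rates below are illustrative assumptions.

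**SAE criterion**

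- Exact (Clopper-Pearson) two-sided 95% upper limit for 0/n: 1 − 0.025^(1/n). For n = 10 this is 1 − 0.692 = 0.308.
- Alternatives for 0/10: one-sided exact 1 − 0.05^(1/10) = 0.259; Wilson two-sided z²/(n + z²) = 3.84/13.84 = 0.278.
- Probability of seeing no SAE, (1 − p)^10: 0.9^10 = 0.349 at p = 10%; 0.8^10 = 0.107 at 20%; 0.7^10 = 0.028 at 30%.

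**Completion target read as an observed proportion of at least 7/10**

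- Exact 95% interval for 7/10: 0.348 to 0.933.
- P(X ≥ 7) at a true rate of 50%: (120 + 45 + 10 + 1)/1024 = 0.172. At 60% it is 0.382; at 70%, 0.650.

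**Can any result exclude a completion rate below 70%?**

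| Completions | Exact two-sided lower limit | Exact one-sided 95% lower limit | Wilson two-sided lower limit | Exact two-sided binomial p against 0.70 |
|---|---|---|---|---|
| 7/10 | 34.8% | 39.3% | 39.7% | 1.00 |
| 8/10 | 44.4% | 49.3% | 49.0% | 0.73 |
| 9/10 | 55.5% | 60.6% | 59.6% | 0.30 |
| 10/10 | 69.2% | 74.1% | 72.2% | 0.039 |

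The p-value for 10/10 is P(10) + P(≤ 3) = 0.028 + 0.011 = 0.039. So 9/10 or fewer excludes a rate below 70% by none of these four methods. At 10/10 the equal-tailed exact interval misses by 0.8 points and the other three succeed.

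**Fewer than 10 dosed.** Section 4.1 sets a ceiling, not a fixed number. With 8 dosed, the upper limit for 0/8 SAEs is 1 − 0.025^(1/8) = 36.9%, and the lower limit for 8/8 completions is 0.025^(1/8) = 63.1%.

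**Both criteria required together.** Take a true SAE risk of 10% and a true completion rate of 90%. P(no SAE) = 0.349 and P(at least 7 complete) = 0.987. Whatever the dependence between them, the chance of meeting both lies between 0.349 + 0.987 − 1 = 0.336 and 0.349. When the infusion itself is well tolerated, adding the completion target hardly tightens the SAE criterion.

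**The case against.** The strongest defence is that Section 10.2 states an expectation, not a decision rule. It uses the language of hypothesis and proposal, and sets no H0/Ha for safety. Where the plan wants a rule it writes one, as with the confidence-limit criterion for a 25% seizure reduction in Section 10.4. The study is declared exploratory, the sample size is openly pragmatic, and an upper limit of 31% follows from 0/10 in any trial. Much of the reporting is already planned: SAE incidence is a primary endpoint, causality is graded (Section 8.2.2), individual data are listed (Section 10.4.10), and Section 10.1 defers details to a separate SAP. The SAE criterion is also not uniformly lenient: it fails 65% of the time at a 10% risk and 89% at 20%.

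Most of this stands as context. It justifies treating 10 subjects, and the point does not ask for more. It does not justify wording in which the absence of SAEs determines that the drug is safe and tolerable, and the text provided plans no interval for either proportion.

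Two stronger readings are tempting and the documents do not support them.

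- A reader might infer that no possible result could establish 70% completion at the plan's own two-sided 5% level. That holds only for the equal-tailed exact interval. The plan names no method for a proportion and specifies no test of 70%, and the exact two-sided binomial test rejects at 10/10.
- A reader might infer that the completion denominator could be the roughly 15 screened instead of the 10 dosed. Section 7.3.2 places enrollment after eligibility is met, and the synopsis speaks of 10 recruited. The ambiguity is limited to eligible subjects who never start the infusion.

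**Conclusion.** The point holds as a fault in the stated conclusion and in the missing intervals, not in the sample size. Under the two-sided 95% convention with exact limits, 0/10 SAEs excludes only risks above about 31%. Completion at the 70% target (7/10) is compatible with rates from 35% to 93%. Only 10/10 could exclude a rate below 70%, and that result is borderline and depends on the method.

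The figures assume that all 10 subjects are dosed and that outcomes are independent between subjects with a common risk. Fewer dosed subjects would widen the limits for a given observed proportion. Ignoring causality is a separate weakness that does not depend on the arithmetic. The seriousness is moderate: the data collected are unaffected, but what may be claimed from them on the primary objective is.

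**What to change.** In Sections 10.2 and 10.4.2, and in the separate SAP:

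- Replace the verdict with estimation. Over Baseline to Week 8, report the proportion of dosed subjects with any SAE and the proportion with a related SAE. Report also the proportion of dosed subjects who complete the infusion. Give each an exact (Clopper-Pearson) two-sided 95% confidence interval.
- Define the denominator as subjects in whom the infusion was started, and state which grades of the Section 8.2.2 causality scale count as related.
- State in advance that 70% completion is a descriptive target, and that 0/10 excludes only SAE risks above about 31%.
- Word the conclusion as *no SAE observed in n dosed subjects (95% CI upper limit x%)* instead of declaring the drug safe and tolerable.

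The cost is a change of wording and three intervals per report. No extra subjects or data are needed. The downside is that the stated conclusion becomes less favourable.
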